1.0 Background

Adult disability services are complicated, fragmented, and difficult to navigate. For parents of individuals with disabilities, it is frustrating to learn different eligibility schemes, apply for services, and actually access appropriate services. It can be especially difficult for Spanish-speaking, Latinx families to access transition services. Given the systemic barriers facing Spanish-speaking Latinx families, they may especially benefit from an advocacy program to help them learn how to access services. Thus, the purpose of this project is to test the feasibility and effectiveness of an advocacy program for Latinx families.

2.0 Rationale and Specific Aims

The purpose of this study is to determine the feasibility and effectiveness of an advocacy program for Latinx families of transition-aged youth with autism. Specifically, we are examining whether the participants feel that the program is acceptable and feasible as well as whether the program increases their advocacy, knowledge, empowerment, and access to services.

3.0 Inclusion/Exclusion Criteria

To be included in the study, the participant must be: over the age of 18, identify as Latinx, have a child with autism who is over the age of 12, speak Spanish, and reside in Illinois.

4.0 Enrollment/Randomization

Upon learning about the program, the participants will click the link to RedCap. The RedCap survey will include the screening questions (see attached). If the participant meets the inclusionary criteria, the participant will then be directed to the consent form. If the participant signs the consent form, they will then be directed to the pre-survey. After completing the pre-survey, the research team will randomize the participant to either receive the advocacy program in the fall of 2023 or the spring of 2024. The research team will notify the participant of their random assignment. We will enroll 50 participants.

5.0 Study Procedures

Upon learning about the program, the participants will click the link to RedCap. The RedCap survey will include the screening questions. If the participant meets the inclusionary criteria, the participant will then be directed to the consent form. If the participant signs the consent form, they will then be directed to the pre-survey. After completing the pre-survey, the research team will randomize the participant to either receive the advocacy program in the fall of 2023 or the spring of 2024. The research team will notify the participant of their random assignment.

During the advocacy program, the participant will complete short formative evaluations at the end of each session. These evaluations will be completed via RedCap. See

attached. At the end of the advocacy program, the participant will receive the summative evaluation (see attached) and post survey link via RedCap (see attached). Six months later, all participants will be asked to complete the follow-up survey (which is identical to the post-survey). Altogether, participation is up to nine months. The follow-up survey will also be administered via RedCap.

6.0 Reporting of Adverse Events or Unanticipated Problems involving Risk to Participants or Others

This is a minimal risk study. We do not expect any adverse events or unanticipated problems. However, if an adverse event or unanticipated problem occurs, it will be immediately reported to the PI. The PI will then notify the IRB immediately (i.e., within 24 hours of learning of the incident).

7.0 Study Withdrawal/Discontinuation

A participant can withdraw from the study at any time. There is no penalty for withdrawing from the study.

8.0 Statistical Considerations

This study is sufficiently powered to discern effects on knowledge, advocacy, empowerment, and unmet service needs. Inferential statistics will be used to gauge the effect of the advocacy program.

9.0 Privacy/Confidentiality Issues

The advocacy program and data collection will occur in private locations. All data will be electronic and stored on password-protected computers of research team members for this project. Participant identifiers will be stored separately from the coded participant data.

10.0 Follow-up and Record Retention

The study participation should be approximately nine months. Data will be destroyed at the conclusion of the study.

Official Title: Adapting an Advocacy Services Intervention for Latinx Families of Transition-aged Youth With Autism Spectrum Disorder

NCT Number: NCT06207149

Document Date: 8/25/23 (date of most recent approval by the human subjects protection review board)

Statistical Analysis Plan: First, we will determine whether there are any missing data and impute as needed following Harrell's guidelines (2000). Then, we will determine whether there are demographic differences between the intervention and control groups; we will control for relevant differences, as needed. For the first research question, we will conduct a MANOVA to discern differences in the post scores on knowledge of adult disability services, advocacy skills and comfort, individual advocacy activities, and the Family Empowerment Scale. For the second research question, we will conduct a repeated measures ANOVA by condition. The dependent variables will be the number of services received and unmet service needs.

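### Covariates are chosen by observed demographic imbalance, and the research question 1 MANOVA of post scores has no pre-score term although a pre-survey precedes randomisation: a cheap gain in precision if that survey carries the scales

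*SAP*

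**What the plan says.** The SAP is one paragraph. After imputation, its rule for covariates is: "we will determine whether there are demographic differences between the intervention and control groups; we will control for relevant differences, as needed". It gives no candidate list, no test or threshold for a difference, and no meaning for a relevant one.

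For research question 1, "we will conduct a MANOVA to discern differences in the post scores on knowledge of adult disability services, advocacy skills and comfort, individual advocacy activities", together with the Family Empowerment Scale. No pre-score covariate or time factor is mentioned. Research question 2, on services received and unmet service needs, is treated differently: "For the second research question, we will conduct a repeated measures ANOVA by condition". The time points for that analysis are not listed.

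The Protocol, section 4.0, fixes the order of events: "After completing the pre-survey, the research team will randomize the participant". Section 5.0 mentions "the follow-up survey (which is identical to the post-survey"), but makes no such statement about the pre-survey, whose content is in an attachment that is not shown. Section 8.0 adds only this on method: "Inferential statistics will be used to gauge the effect of the advocacy program". Enrolment is 50 (section 4.0).

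**The concern.** There are two linked weaknesses.

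**The covariate rule.** If randomisation is sound, a demographic difference between arms is a chance event and says nothing about whether the variable predicts the outcome. Even if relevance is read as prognostic value, a variable enters only after a difference is seen, so a strong predictor that happens to balance stays out. With no threshold or list, two analysts following the SAP could fit different models.

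**The missing pre-score.** The rule covers demographics only, so it cannot bring in the pre-survey value of each outcome, which is usually the best available predictor of the post score. With 50 participants and a power statement in Protocol section 8.0 that carries no figures, precision in research question 1 is what is at stake.

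**Working it through.** The documents give no power calculation to reproduce, so the figures below are an illustration for a single outcome.

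**Inputs**
- From the Protocol: 50 participants in total (section 4.0) and a pre-survey before randomisation (sections 4.0 and 5.0).
- Assumed, because neither document states them: 25 per arm, all analysed; true difference d = 0.5 in post-score SD; two-sided 0.05; pre/post correlation r = 0.3, 0.5 or 0.7; the pre-survey carries the same scales.

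**Step 1. Unadjusted comparison.** Two-sample t test with 50 − 2 = 48 df and noncentrality d × √(25/2) = 0.5 × 3.536 = 1.768. Power is 41.0%. The difference detectable with 80% power is 0.81 SD.

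**Step 2. Four pre-scores as covariates.** Error df are 48 − 4 = 44. The outcome's own pre-score reduces the residual variance to (1 − r²); the other three are assumed to add nothing. The noncentrality is 1.768 × √(1 − B) / √(1 − r²), where B is the chance imbalance in the four pre-scores, distributed Beta(4/2, 45/2). Power is averaged over B.

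| Pre/post r | Residual variance | Power, four pre-scores | Power, own pre-score only (47 df) | Detectable at 80%, four pre-scores |
|---|---|---|---|---|
| Unadjusted | 1.00 | 41.0% | 41.0% | 0.81 SD |
| 0.3 | 0.91 | 41.2% | 43.5% | 0.81 SD |
| 0.5 | 0.75 | 48.1% | 51% | 0.73 SD |
| 0.7 | 0.51 | 64.0% | 67% | 0.60 SD |

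The four-pre-score column is the one that matches the model proposed below.

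**Step 3. Break-even.** With N = 50 and k covariates, chance imbalance inflates the variance of the treatment difference by (N − 3)/(N − 3 − k). For k = 4 this is 47/43 = 1.093. Adjustment breaks even when (1 − r²) × 47/43 = 1, so r = √(1 − 43/47) = √0.0851 = 0.29. Below that there is a small loss.

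**Step 4. The imbalance rule by itself.** The chance of at least one difference with p < 0.05 among k independent demographic tests is 1 − 0.95^k: 19% for k = 4 and 40% for k = 10. The rule was simulated with ten weak demographics (correlations with the outcome evenly spaced from 0 to 0.2; inter-item correlation 0 or 0.3; 20,000 runs per setting):

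| Threshold (assumed) | Power at d = 0.5 | Type I error |
|---|---|---|
| p < 0.05 | 39–40% | 4.8–4.9% |
| p < 0.2 | 37–38% | 4.2–4.6% |

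Unadjusted power in the same runs was about 41%. A separate simulation of one strongly prognostic covariate, entered only if p < 0.05, gave type I error of 4.3% (r = 0.5) and 3.7% (r = 0.7). The rule, applied mechanically, is conservative.

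**Step 5. The joint test.** Simulation of the four-outcome test with all four effects at 0.5 SD gave unadjusted power of about 75–78%, 47% and 32% at assumed inter-scale correlations of 0, 0.3 and 0.6. Adding the four pre-scores gave no gain at r = 0.3, about 4–9 points at r = 0.5 and about 20–26 points at r = 0.7. The level depends heavily on correlations that the documents do not give; the direction matches Step 2.

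**The case against.** The strongest reply has three parts, and much of it stands.

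First, comparing post scores between randomised arms is valid and unbiased, so adding pre-scores is a matter of efficiency. That is correct. A reader might infer that the plan biases the comparison or inflates type I error; the documents do not support either. Randomisation protects the post-score comparison, and Step 4 shows error rates at or below 5%. A reader might also infer that the SAP proposes to settle the model after seeing the results. It does not say so; its wording merely leaves room for it.

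Second, the larger numbers depend on an instrument that cannot be seen. This also stands. It is tempting to treat the pre-survey as known to carry the four scales, but the Protocol states identity only between the follow-up and post surveys. The aim in Protocol section 2.0, to see whether the program raises knowledge, advocacy and empowerment, makes it likely, not certain. Nor can one say that the SAP ignores pre-survey data altogether: the research question 2 repeated measures analysis may already use the pre-survey as a time point, so the pre-score point concerns research question 1 only.

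Third, 41% is a single-outcome figure and does not describe the planned joint test. That is right, as Step 5 shows, and it should not be quoted as the power of research question 1. The direction and rough size of the gain still carry over.

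What the reply does not remove is that nothing in either document fixes the covariate model, and that a better-specified one needs only a change of wording.

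**Conclusion.** The point holds as a cheap improvement. The certain part, that covariates are selected by observed imbalance under open wording, has a small effect: about 1 to 4 percentage points of power in the illustration. The larger part is conditional on the pre-survey carrying the four research question 1 scales. In that case the post-score-only analysis gives up nothing at a pre/post correlation of 0.3, about 7 points of power at 0.5 (48.1 − 41.0) and 23 points at 0.7 (64.0 − 41.0) for one outcome. These sizes rest on the assumed equal allocation, full follow-up, effect of 0.5 SD and two-sided 0.05. If the scales are not in the pre-survey, the point reduces to the covariate rule.

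**What to change.** Confirm in the SAP whether the pre-survey carries the four research question 1 scales, and make two replacements.

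Replace the covariate sentence with:

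> Baseline characteristics are tabulated by arm and are not used to choose the model. Demographic covariates enter only if named here in advance on prognostic grounds; any other adjustment is a labelled sensitivity analysis.

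Replace the research question 1 sentence with:

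> The four post scores are compared between arms by MANCOVA with the four corresponding pre-survey scores as covariates, whatever the observed balance. If the pre-survey does not carry these scales, the four post scores are compared by MANOVA.

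The second sentence of that text is needed so that research question 1 keeps an analysis in either case. Leave the research question 2 sentence unchanged.

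Cost: wording only, with no new data if the scales were collected. The statistical price is four error degrees of freedom (48 to 44 with 50 analysed), hence the break-even at a correlation of about 0.29 and a small loss below it.

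### The research question 1 MANOVA uses post scores only; if the pre-survey holds the same scales, leaving the pre-scores out loses precision once the pre-post correlation is moderate.

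*SAP*

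**What the plan says.** The SAP's analysis for research question 1 reads "we will conduct a MANOVA to discern differences in the post scores on knowledge of adult disability services". The other three outcomes in the same test are the Family Empowerment Scale, individual advocacy activities, and advocacy skills and comfort. Before that it says "we will determine whether there are demographic differences between the intervention and control groups; we will control for relevant differences, as needed". No pre-survey score is named as a covariate or as a repeated measure. A repeated measures ANOVA is planned, but only for research question 2 (services received and unmet service needs).

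Protocol section 4.0 fixes the timing of the pre-survey: "After completing the pre-survey, the research team will randomize the participant". Section 5.0 repeats this and says that the follow-up survey is identical to the post-survey. It does not say whether the pre-survey is. Section 2.0 states the aim as "whether the program increases their advocacy, knowledge, empowerment, and access to services".

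Section 4.0 sets enrolment at 50. Section 8.0 says the study is sufficiently powered and gives no effect size, SD, alpha or power.

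**The concern.** If the pre-survey carries the four scales, each participant has a score on every research question 1 outcome from before randomisation. Such a score is usually a strong predictor of the post score, and the planned model does not use it. The covariate rule does not fill the gap. It concerns demographic differences, and even a generous reading would make adjustment depend on the imbalance seen in the data.

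The planned comparison is unbiased over repeated randomisations and its type I error holds. What is at stake is the width of the intervals and the chance of detecting an effect in a trial of 50. In any one trial, a chance baseline gap also carries into the post-score difference at about the pre-post correlation times the gap. This is the same loss of precision seen from another side, not a second harm.

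**Working it through.** **Inputs from the documents.** Total enrolment 50 (protocol 4.0); four outcomes in one MANOVA (SAP); pre-survey completed before randomisation (protocol 4.0 and 5.0).

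**Assumptions, because the documents give no figure.** 1:1 allocation, so n = 25 per arm; two-sided alpha 0.05; no dropout, with 20 per arm as a sensitivity case; true effect d = 0.5 SD on every scale; correlation 0.5 between outcomes; pre-post correlation r = 0.3, 0.5 or 0.7, with 0.1 as a low case; the pre-survey holds the four scales.

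**The plan's own figure.** The target of 50 cannot be reproduced, because section 8.0 gives no inputs. Solving backwards, a two-sample t test with 25 per arm has 80% power for d = 0.81.

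**Single scale.** Adjusting for a scale's own pre-score multiplies the residual variance by 1 − r², which is 0.91, 0.75 or 0.51. Power comes from the noncentral t with noncentrality d·√(n/2)/√(1 − r²), with 48 df post-only and 47 df adjusted. The interval half-widths come from simulation. As a check on the first, t(0.975, 48 df) × √(2/25) = 2.011 × 0.283 = 0.57.

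| | Post-only | r = 0.3 | r = 0.5 | r = 0.7 |
|---|---|---|---|---|
| Detectable effect at 80% power (SD) | 0.81 | 0.77 | 0.70 | 0.58 |
| Power at 0.5 SD | 41% | 44% | 52% | 68% |
| Mean 95% CI half-width (SD) | 0.57 | 0.55 | 0.50 | 0.41 |
| Equivalent unadjusted total, 50/(1 − r²) | 50 | 55 | 67 | 98 |

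**Four outcomes, closed form.** The Hotelling T² test is a noncentral F with λ = (n/2)·d′S⁻¹d/(1− r²). With four equal effects and a common correlation of 0.5, d′S⁻¹d = 4 × 0.25/(1 + 3 × 0.5) = 0.40. Post-only λ is therefore 12.5 × 0.40 = 5.0, on F(4, 45). With four covariates λ is 5.0/0.91 = 5.5, 5.0/0.75 = 6.7 or 5.0/0.51 = 9.8, on F(4, 41).

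**Four outcomes, simulated.** The closed form counts the lost degrees of freedom but not the variance added by chance imbalance in four covariates, so it flatters adjustment. A simulation of 20,000 trials per cell (Wilks test, post = r·pre + √(1 − r²)·error) includes that cost and is the better guide.

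| Power of the four-outcome test | Post-only | r = 0.1 | r = 0.3 | r = 0.5 | r = 0.7 |
|---|---|---|---|---|---|
| 25 per arm, closed form | 36% | 36% | 39% | 47% | 65% |
| 25 per arm, simulated | 36% | 33% | 36% | 42–43% | 61% |
| 20 per arm, simulated | 28% | – | 27–28% | 33% | 47–48% |

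Ranges show the spread between repeat simulations. With 25 per arm, null rejection was 5.2% post-only and 5.1% with covariates, so both tests hold their level.

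**Chance baseline gap.** The standard error of the baseline difference is √(2/25) = 0.283 SD. A gap of 0.3 SD or more in either direction has probability 29% on each scale. Such a gap shifts the post-only estimate by about 0.3 × r, which is 0.09, 0.15 or 0.21 SD at r = 0.3, 0.5 or 0.7.

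**The case against.** The strongest reply has three parts.

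*The premise cannot be checked.* The survey attachments are not in the public text, and only the post and follow-up surveys are called identical. This stands. The wording of the aim as an increase and the term post scores make shared scales plausible but do not prove it. The finding is therefore conditional, and the fix begins by asking for the content of the pre-survey.

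*The planned test is valid.* This also stands. No conclusion drawn from the post-only MANOVA would be wrong in its error rate, and chance baseline gaps are already covered by its intervals. The issue is efficiency alone.

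*Four covariates cost a lot with 50 participants.* This stands in part. The MANCOVA gains nothing at r = 0.3, loses about 3 points of power at r = 0.1, and with 20 per arm is level to about one point lower at r = 0.3. The benefit appears from about r = 0.4 (39% against 36%) and is large only near 0.7. The per-scale ANCOVA, which spends one degree of freedom, gains a little even at r = 0.3 (44% against 41%).

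The omission may also be brevity in a one-paragraph SAP rather than a decision. Even so, a reader cannot tell from the text that baseline scores will be used.

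**Conclusion.** The concern holds. The research question 1 model leaves out scores that are probably collected before randomisation, and its only adjustment rule covers demographics and depends on the data. The consequence is a loss of precision, not of validity. With 25 per arm and r between 0.3 and 0.7, own-score adjustment cuts the variance of a single-scale comparison by 9% to 49%. For the four-outcome test the gain is nil at r = 0.3, about 6 to 7 points of power at r = 0.5 and about 25 points at r = 0.7.

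This rests on the pre-survey containing the four scales and on assumed values for r, alpha, allocation, effect size and the correlation between outcomes. The change should be made, but it is not essential to the validity of the trial. Confidence is medium because the instruments are not shown.

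**What to change.** In the SAP:

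1. State whether the pre-survey contains the four research question 1 scales.
2. If it does, prespecify the four pre-survey scores as covariates in the multivariate test (MANCOVA), whether or not the arms differ at baseline.
3. For each scale, prespecify the adjusted mean difference and 95% CI from an ANCOVA of post score on arm and that scale's own pre-score.

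Replacing the multivariate test with Holm-adjusted ANCOVAs is optional and a trade-off. At Holm's first step (alpha 0.05/4 = 0.0125), single-scale power at 0.5 SD is 24%, 30% or 46% at r = 0.3, 0.5 or 0.7.

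The cost is SAP wording, with no new data collection if the scales are in the pre-survey. Statistically it takes four residual degrees of freedom in the MANCOVA, or one in each ANCOVA, and gives up about 3 points of MANCOVA power if r turns out to be 0.1 or less.

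### The aim asks which outcomes improve, but the SAP plans only an omnibus MANOVA on four post scores and gives no outcome-level estimates, no use of the pre-survey and no multiplicity rule

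*SAP*

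**What the plan says.** Protocol section 2.0 sets the effectiveness aim as "whether the program increases their advocacy, knowledge, empowerment, and access to services". That names several outcomes and a direction for them.

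For the first research question the SAP states "we will conduct a MANOVA to discern differences in the post scores on knowledge of adult disability services, advocacy skills and comfort", and completes the list with "individual advocacy activities, and the Family Empowerment Scale". That is one multivariate test on four post scores. For the second question, "we will conduct a repeated measures ANOVA by condition", and "The dependent variables will be the number of services received and unmet service needs".

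The SAP allows control for demographic differences between groups, but does not name the pre-survey scores as covariates in the MANOVA. Neither document names a primary outcome, an alpha, a follow-up test, an effect estimate or a multiplicity rule. Protocol section 8.0 adds only "This study is sufficiently powered to discern effects on knowledge, advocacy, empowerment, and unmet service needs" and a general reference to inferential statistics. On size and design, section 4.0 says "We will enroll 50 participants" and "the research team will randomize the participant to either receive the advocacy program in the fall of 2023 or the spring of 2024"; the pre-survey is completed before randomization.

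**The concern.** A two-group MANOVA asks whether any linear combination of the four scores differs between arms. A significant result does not identify the outcome or the sign, and carries no mean difference or interval. The aim needs all three.

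This leaves two ways to proceed:

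- **MANOVA only.** The error rate is 5%, but no outcome-level answer follows.
- **MANOVA followed by separate tests.** An answer follows, but the SAP has no rule for those tests. A common default is to test each outcome at 5% once the MANOVA is significant. That protects against false claims when all four nulls are true. Once one outcome responds, the gate tends to open and the other three are each tested at the full 5%.

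The second question adds two outcomes with neither an order nor an adjustment. With no primary outcome anywhere, any single significant result could be presented as evidence of effectiveness.

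**Working it through.** **Inputs from the documents:** total 50 (protocol 4.0); four scores in the MANOVA and two services variables (SAP). No error rate, effect size or alpha is stated, so there is no plan figure to reproduce.

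**Assumptions:** 1:1 allocation, so 25 per arm, with 20 per arm to allow for dropout; two-sided 5%; normal scores with a common correlation ρ of 0, 0.3, 0.5 or 0.7; one outcome with a true effect of *d* SD and three with none; each services outcome tested separately at 5%.

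**1. Ceiling without a gate.** Three true-null outcomes at 5% each: 1 − 0.95³ = 14.3% if independent. By simulation the figure is about 13.6% at ρ = 0.3, 12.5% at 0.5 and 10.9% at 0.7.

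**2. With the MANOVA as gate.** The gate is T² = (n/2)·D′S⁻¹D, where D is the vector of mean differences and S the pooled covariance. F = T²(2n − 5)/[4(2n − 2)] is referred to 4 and 2n − 5 degrees of freedom. Unadjusted t tests follow only if F is significant. The table gives the chance of at least one false claim on a null outcome (40,000 trials per setting, simulation error about 0.2 points; ranges are over ρ = 0 to 0.7).

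| Effect on the one responder | 25 per arm | 20 per arm |
|---|---|---|
| none (all four null) | about 3 to 5% | about 3 to 5% |
| 0.5 SD | 8.0 to 9.0% | 7.3 to 8.2% |
| 0.8 SD | 10.7 to 11.8% | 10.6 to 11.1% |
| 1.0 SD | 11.1 to 13.5% | 11.1 to 12.7% |
| 1.2 SD or more | 10.8 to 14.5% | 10.9 to 14.4% |

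The overall range with one responder is about 7 to 14%. In the first row the rate cannot exceed the MANOVA's own 5%. Figures of 12 to 14% need an effect of about 1.0 SD or more and ρ of 0.5 or less.

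**3. Holm across the four.** In the same one-responder settings at 25 per arm, the chance of any false claim is 3.3 to 5.0%.

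**4. Services outcomes.** Two tests at 5%: 1 − 0.95² = 9.75% if independent, about 9.0% at ρ = 0.5 and 8.3% at ρ = 0.7. Holm brings this to 5% or less (both null and independent: 1 − 0.975² = 4.9%).

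**5. What the fix gives up.** With one responder, the MANOVA's noncentrality is λ = (n/2)·d²·(1 + 2ρ)/[(1 − ρ)(1 + 3ρ)]. For n = 25 and d = 0.8, (n/2)d² = 8:

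- ρ = 0.3: λ = 8 × 1.6/(0.7 × 1.9) = 9.62, MANOVA power about 0.65
- ρ = 0.5: λ = 8 × 2.0/(0.5 × 2.5) = 12.8, power about 0.78
- ρ = 0.7: λ = 8 × 2.4/(0.3 × 3.1) = 20.6, power about 0.95

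Holm tests without baseline adjustment identify that outcome with probability about 0.59 to 0.60 throughout.

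**6. When all four rise 0.6 SD** (25 per arm): MANOVA power is about 0.64 at ρ = 0.3 and 0.50 at ρ = 0.5. At least one Holm-significant outcome occurs in about 0.70 and 0.63.

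**The case against.** The strongest reply is that the SAP contains no follow-up tests. A reader might infer that the plan itself carries a 12 to 14% false-claim rate. It does not: the MANOVA followed literally has a 5% error rate and makes no outcome-level claims. The inflation belongs to a procedure that analysts might add, and its size depends on effect and correlation values that the documents do not give. This stands, and the figure must stay conditional. It also falls with more responders: about 7.4 to 7.9% with two at 0.5 SD, and about 5% with three at 0.8 SD.

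A reader might also infer that a significant MANOVA could hide harm. If two outcomes rose and one fell by 0.6 SD each, the MANOVA would be significant in about 92 to 98% of trials (25 per arm, ρ = 0.3 to 0.5). That shows the test is non-directional, but nothing in the documents suggests that the program lowers any outcome. Group means would show the sign, if the SAP required them to be reported.

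Separate alpha for separate research questions is a defensible convention, so the lack of adjustment across the two questions is not in itself an error.

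The power comparison is mixed. In the case where all four rise 0.6 SD, Holm's advantage concerns finding at least one outcome; power for each single outcome is only about 39%.

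None of this supplies an outcome-level analysis. Nor does treating the trial as a feasibility study excuse the gap, since section 8.0 claims adequate power for effects on named outcomes.

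**Conclusion.** The point holds as a gap in specification. The first-question analysis does not match the aim: it yields no outcome-level estimate, direction or interval, and it leaves the pre-survey scores out of the MANOVA. This follows from the text alone.

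The error figures are conditional. The 7 to 14% applies if unadjusted 5% follow-ups were used and exactly one outcome responded by 0.5 SD or more, with 20 to 25 per arm, 1:1 allocation and correlation 0 to 0.7. Every one-responder setting tried exceeded 5%; with no responder the rate stays below 5%. The 9.75% for the services outcomes assumes independence and separate tests at 5%.

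The documents do not support the stronger reading that the SAP plans unadjusted follow-ups, or that the MANOVA is invalid as a test of overall difference. This is a cheap improvement.

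**What to change.** - Replace the MANOVA as the first-question analysis with four post-survey comparisons by arm. Adjust each for that outcome's own pre-survey score and report it as a mean difference with a 95% CI.
- Apply Holm across the four. Keep the MANOVA, if wanted, as descriptive only and not as a gate.
- Apply Holm across the two services outcomes.
- State alpha and sidedness, and say that error is controlled within each question, not across both. Two families at 5% leave 1 − 0.95² = 9.75% across the two if independent.

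The cost is SAP wording; the pre-survey is already collected. The downside is power in one case. When a single outcome moves 0.8 SD, the MANOVA rejects more often (about 0.65, 0.78 and 0.95 at correlation 0.3, 0.5 and 0.7) than Holm identifies that outcome (about 0.59 to 0.60 before baseline adjustment), although its rejection says only that something differs. Baseline adjustment should recover some power. How much depends on the pre-to-post correlation *r*, through a residual variance factor of about 1 − r², and the documents do not give *r*.

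### If the repeated measures ANOVA for services received and unmet needs is the pre/post interaction test, it is a change-score test; adjusting the post-survey comparison for the pre-survey value would usually be more precise

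*SAP*

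**What the plan says.** The SAP's analysis for the second research question is "For the second research question, we will conduct a repeated measures ANOVA by condition". On outcomes it adds: "The dependent variables will be the number of services received and unmet service needs". It does not say which waves enter, whether the condition-by-time interaction or another term is the test, or what effect estimate will be reported. The only covariate adjustment it mentions concerns demographic differences between the groups: "we will control for relevant differences, as needed". The pre-survey value of the outcome is not named as a covariate.

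Protocol section 4.0 puts the baseline measurement before allocation: "After completing the pre-survey, the research team will randomize the participant". The two arms differ in start date, since the team will "randomize the participant to either receive the advocacy program in the fall of 2023 or the spring of 2024". The sample is small: "We will enroll 50 participants".

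Protocol section 5.0 describes two later surveys. The first is tied to program completion: "At the end of the advocacy program, the participant will receive the summative evaluation (see attached) and post survey link via RedCap". The second is the follow-up: "Six months later, all participants will be asked to complete the follow-up survey (which is identical to the post-survey").

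**The concern.** In a randomized comparison with one pre and one post measurement, the condition-by-time interaction of a repeated measures ANOVA is the difference between arms in mean change. That subtracts the whole pre-survey value from the post-survey value, as if the slope of post on pre were 1. When the slope is below 1, as it is with equal variances and any correlation short of 1, the subtraction adds noise. A linear model with arm and the pre-survey value estimates the slope and targets the same between-arm difference.

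Access to services is one of the stated aims (Protocol section 2.0), and section 8.0 asserts adequate power for unmet needs without giving a calculation. With 50 participants, precision available from a measurement already in hand is worth taking.

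**Working it through.** **Stated figure.** The only design number is 50 participants. It cannot be reproduced, because no effect size, SD, alpha, correlation or power is given.

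**Inputs.** From the documents: N = 50, two arms, pre-survey before randomization. Assumed: 1:1 allocation (25 per arm), two-sided alpha 0.05, no dropout, approximate normality, a between-arm difference of 0.6 SD at the post-survey, and r from 0.3 to 0.9.

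**Step 1: equivalence.** For two waves, the interaction F equals the squared t statistic on change scores. A direct computation on one simulated data set gave 2.505 for both.

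**Step 2: variances.** With equal pre and post variances, in units of the outcome variance:
- post-survey only: 1
- change score: 2(1 − r)
- baseline-adjusted: 1 − r²

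The adjusted-to-change ratio is (1 − r²) / [2(1 − r)] = (1 + r)/2. Estimating the slope at N = 50 multiplies this by about 47/46 = 1.02.

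| r | Change | Adjusted | Ratio | Ratio with slope cost |
|---|---|---|---|---|
| 0.3 | 1.40 | 0.91 | 0.65 | 0.66 |
| 0.5 | 1.00 | 0.75 | 0.75 | 0.77 |
| 0.7 | 0.60 | 0.51 | 0.85 | 0.87 |
| 0.9 | 0.20 | 0.19 | 0.95 | 0.97 |

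With the slope cost, the ratio reaches 1 at r of about 0.95 to 0.97.

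**Step 3: power at 0.6 SD.** The noncentrality is (25/2) × 0.6² = 4.5 divided by the variance factor. At r = 0.5 that is 4.5/1.00 = 4.50 for the change score on F(1,48), and 4.5/(0.75 × 47/46) = 5.87 for the adjusted model on F(1,47). For the three-wave interaction under compound symmetry it is 4.5 × (2/3)/(1 − r) on F(2,96), which is 6.00 at r = 0.5. The factor 2/3 is the same whether the arm difference over pre, post and follow-up is (0, d, 0) or (0, d, d).

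| r | Pre/post interaction | Three-wave interaction, 2 df | Adjusted post-survey |
|---|---|---|---|
| 0.3 | 0.42 | 0.43 | 0.58 |
| 0.5 | 0.55 | 0.57 | 0.66 |
| 0.7 | 0.77 | 0.80 | 0.82 |
| 0.8 | 0.91 | 0.94 | 0.93 |

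At 0.8 SD and r = 0.5, the pre/post interaction has 0.79 and the adjusted model 0.89.

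**Step 4: unequal variances.** If the post-survey SD is k times the pre-survey SD, the ratio before slope cost is k²(1 − r²) / (1 + k² − 2rk). With k = 1.25 (an assumption):
- r = 0.5: 1.172/1.3125 = 0.89
- r = 0.7: 0.797/0.8125 = 0.98
- r = 0.8: 0.5625/0.5625 = 1.00

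**Step 5: three-wave contrast with one degree of freedom.** The mean of post and follow-up minus pre has variance 1.5(1 − r). If the arm difference persists undiminished at follow-up, the ratio of adjusted post-survey variance to this is (1 + r)/1.5, which passes 1 at r = 0.5. At r = 0.7 and 0.6 SD, power is 0.87 for this contrast and 0.82 for the adjusted post-survey model.

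**The case against.** The strongest reply is that the SAP does not commit to a two-wave interaction. Three surveys are collected, and with all three the analysis is not a change-score test. The advantage of the adjusted post-survey model is then smaller and can vanish: the omnibus interaction is level or slightly ahead from about r = 0.8, and a one-degree-of-freedom contrast using the follow-up wave is more precise above r = 0.5 if the arms still differ then. That stands as a limit on the claim. It does not rescue the plan. The omnibus test has two degrees of freedom and gives no single effect estimate. The other contrast needs a difference that lasts to follow-up, which cannot be assumed when the control arm itself receives the program in spring 2024.

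A second reply is that the adjusted contrast relies on a spring-arm post-survey taken before that arm's program, while Protocol section 5.0 ties the post-survey to program end and gives the spring arm no separate timing. This is correct and has to be settled. It applies equally to the planned ANOVA, so it does not favor one analysis over the other.

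A third reply is that the gain rests on unknown values. This also stands: with a post-survey SD 1.25 times the pre-survey SD, most of it disappears at r = 0.7.

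A reader might go further and infer that the plan wastes the pre-survey, that it yields no estimate, or that the change costs nothing. The documents and arithmetic do not support these. A change score does use the pre-survey and, with equal variances, is more precise than a post-only comparison when r exceeds 0.5. The difference in mean change is an estimate in service units. Adjustment costs a degree of freedom.

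**Conclusion.** The point holds in conditional form. The SAP leaves the waves and the tested term open. On the pre/post reading, the planned test remains valid under randomization but is usually less precise than a comparison adjusted for the pre-survey value. With equal variances and the slope cost included, adjustment lowers the variance by about 34%, 23% and 13% at r = 0.3, 0.5 and 0.7. At 0.6 SD that is worth about 0.16, 0.11 and 0.06 in power (0.577 − 0.420, 0.660 − 0.547 and 0.821 − 0.765). The three-wave omnibus interaction is also behind up to about r = 0.7.

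This is an efficiency recommendation, not a finding of bias, and it does not establish that the SAP intends a change-score test. The correlation, effect size, alpha and 1:1 allocation are assumptions, and normal theory is only approximate for count outcomes, so the powers are illustrative.

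**What to change.** Replace the SAP sentence on the second research question with wording to this effect: for each of the two outcomes, the test of efficacy is the difference between arms at the post-survey, estimated from a linear model with arm and the pre-survey value of that outcome, and reported with a 95% confidence interval; six-month data are reported separately and are not part of the efficacy test.

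Before adopting it, confirm and write into Protocol section 5.0 that the spring arm completes its post-survey before its own program starts. If that survey is not scheduled, neither this contrast nor the planned ANOVA gives a comparison with an untreated control at the post-survey.

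This is a cheap improvement: one sentence in the SAP, using a pre-survey already collected. The downsides are one degree of freedom (about 2% of variance at N = 50) and leaving the follow-up wave out of the efficacy test.
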